4.0 HYPOTHESES

We hypothesize that the use of Ready-Heat® blanket will be feasible in this pilot RCT (according to the primary outcome measure) in severely injured trauma patients to whom a MHP is activated while in the trauma bay.

5.0 STUDY METHODS

5.1 Study Design

This will be a pilot, feasibility, prospective, open-label (with blinded outcome assessors) RCT to evaluate the feasibility of using two Ready-Heat® half blankets to increase temperature by at least 1°C at eight hours from arrival to the trauma bay, in severely injured bleeding trauma patients where a MHP is activated. A total of 74 participants will be randomized in a 1:1 ratio, to receive the intervention - two Ready-Heat® 4-panel half blankets applied indirectly (as per manufacturer's directions) with two flannel blankets placed under them, or the control - two warmed blankets (current standard of care) only. The study will take place at Sunnybrook Health Sciences Centre (SHSC). The patient will be screened in the trauma bay and enrolled by the TTL. Upon confirming eligibility for the study, a study research coordinator/assistant will randomize using a web-based randomization sequence built into REDCap. If the patient is randomized to receive the intervention, two Ready-Heat® blankets will be activated by opening the seal on the packaging and affixed to the blood product cooler to be given to the trauma team in the trauma bay. As this is an open-label trial, only the statistician will remain blinded during the final analysis. Enrollment will occur during weekdays between 0800-2000hrs with the aim of assessing feasibility of using the blanket when study coordinators are not always available to reinforce temperature monitoring, proper blanket placement, and compliance with keeping the blanket on the patient over the intervention period. Subjects in the control arm will have two warmed blankets obtained from a blanket warmer appliance in the trauma bay and will be applied on the patient by the trauma team. Temporary removal of the blanket and partial exposure of the patient may be necessary to facilitate clinical procedures. In the intervention arm, two separate four-panel blankets will be used to allow for temporary exposure for clinical procedures while still maintaining coverage for the rest of the body (i.e., 1 four-panel blanket can be applied to the torso while a fractured femur is reduced). Clinicians will be educated to keep the intervention warmer on the patient until 8 hours from time of blanket application. If there is a need to remove the intervention prior to the completion of 8 hours, the clinical team will document the reason (e.g., adverse reaction, interference with procedure, etc.). In this case, clinical teams will be educated to transition to the current standard of care (warmed blankets or

FAWB). If at least one of the two blankets remained until 8 hours post blanket application, clinical teams will be instructed to remove them and apply the current standard of care.

5.2 Study Population

Patients included in this study are severely injured adult trauma patients, admitted to the trauma bay at SHSC as trauma team activations (TTA), where a MHP is activated by the TTL or delegate, within the period the patient is assessed and managed in the trauma bay.

5.2.1 Inclusion Criteria

1. Age \geq 16 years
2. MHP activated in the trauma bay (see Table 1)
3. Between 08:00-20:00hrs on weekdays

Table 1 MHP Activation Criteria

MHP activation criteria

• Life-threatening bleeding situation requiring mobilization of blood bank, laboratory and clinical resources.• Anticipated need for at least 4 units of red blood cells immediately and component therapy (platelets, plasma, and fibrinogen).

5.2.2 Exclusion Criteria

1. Transferred from another healthcare facility
2. Death in the trauma bay prior to randomization
3. Arrival to trauma bay with ongoing CPR
4. Patients with penetrating head injury with Glasgow Coma Scale of 3 AND loss of brain matter through the wound

5.3 Study Activities

5.3.1 Patient screening, recruitment, and enrolment

Recruitment will occur in the trauma bay during weekdays between 08:00-20:00hrs by Staff Trauma Team Leaders, with experience in QI initiatives and enrollment of severely bleeding trauma patients in clinical trials. Due to the high acuity of the patient condition, who usually needs multiple emergent interventions, consent will be obtained retrospectively (delayed consenting process). In addition, by seeking the patient's consent for enrollment during a tenuous point in their care, there is a potential of introducing bias, or concerns about coercion into accepting any care related to the initial resuscitation.

As soon as possible, following the randomization and inclusion, the patient (if able to comprehend) or substitute decision maker (SDM), will be approached about the study. They will have their specific warming intervention explained, and will have, at that point, the right to request that their data are withdrawn from the study.

Study personnel will contact the MRP for permission to approach the patient or ask that they introduce the study to the patient. With permission to enter the patient's circle of care, the research coordinator will then approach patients who were randomized and included in the study. The research coordinator will introduce the trial, confirm eligibility and conduct the informed consent discussion. This discussion will include the rationale for the study, the anticipated risks and benefits of participation, and their rights as a study participant (including withdrawal at any time). Capable participants will be offered an opportunity to ask questions and consult with their family and/or their physician before making a decision to continue in the study. If the patient is deemed incapable of providing informed consent for the study, study personnel will approach the SDM and go over the same process to obtain the consent. Patients or SDM will be given an Informed Consent Form to be signed, at this point.

One signed copy of the informed consent will be placed in the participant's medical record, another copy given to the participant and the original kept in the study file with the research coordinator. If the participant does not wish to participate, the reason for declining will be documented.

Patients will be randomized upon activation of the MHP according to a computer-generated allocation sequence using RedCap. If the patient is randomized to receive the intervention, the study research coordinator/assistant will activate the two Ready-Heat® blankets by opening the seal on the packaging. A trauma team member will place the blankets on the patient. As this is an open-label trial, only the statistician will remain blinded during the final analysis. Enrollment will occur 08:00-20:00hrs on weekdays with the aim of assessing feasibility of using the blanket when study coordinators are not always available to reinforce temperature monitoring, proper blanket placement, and compliance with keeping the blanket on the patient over the intervention period.

Data will be collected by the research assistants and medical students as the patients are enrolled in the trial during weekdays 8 am to 8 pm. REDCap will be used to register the collected variables.

Research Ethics Board (REB) approval of the protocol and the informed consent form will be obtained. A recruitment log of eligible and ineligible patients as well as reasons for non-consent will be kept. We anticipate that this study will take 24 months to complete.

5.3.2 Randomization and stratification

The patient will be screened in the trauma bay and randomized by the study research coordinator/assistant. Patients will be allocated to a treatment group using a secure, concealed, computer-generated, web-based (created on REDCap) randomization sequence. Only a non-study biostatistician will have access to the randomization sequence within the treatment allocation schedule (the study biostatistician will be blinded to treatment allocation for any interim analyses performed). A 1:1 randomization ratio will be used.

5.3.3 Interventions

A schematic representation of the protocol summary is shown in Figure 1.

5.3.3.1 Investigational Products

Ready-Heat® is manufactured by TechTrade LLC¹³. The manufacturer has confirmed the authorized use of this product in Canada, which was a requirement for STAYWARM-1. Further, this product is now currently distributed by Canadian vendors for the Canadian marketplace.

In the attached document from the manufacturer, this device is considered a “Class I medical device”. As such, there is no requirement to obtain an investigational testing authorization (ITA)

Requirements for an Investigational Testing Authorization (ITA)	
Class I	There is no requirement to obtain an ITA for a Class I medical device. Subsection 80(3) of the Regulations permits a manufacturer or importer of a Class I medical device to sell the device to a qualified investigator for the purpose of conducting investigational testing. The manufacturer or importer is still required to possess all the records and information detailed in section 81. Institutional requirements and Research Ethics Board (REB) approval apply.

Adobe Acrobat
Document

The Ready-Heat® product comes in a variety of configurations. The 4-panel blanket is a single-use disposable blanket that uses proprietary air-activated warming panels that provide slow continuous and consistent warming. Weighing 794 grams, and dimensions of 86cm/122cm, each blanket is stored in an oxygen-free poly-bag. Upon opening the package, it gradually heats up to 40°C over a period of 15-20 minutes, and after reaching peak temperature will remain warm for 10 hours.

5.3.3.2 Packaging

Two individually wrapped 4-panel Ready-Heat® blankets will be issued to patients enrolled in the intervention arm. The two individual packages, containing one blanket each, will be opened by the study research coordinator/assistant upon patient randomization to initiate the air-activated exothermic process.

5.3.3.3 Treatment Assignment Procedures

Once enrolled, patients will be randomized to either the control or intervention arm through the randomization procedure described in section 5.3.2.

5.3.3.4 Control arm

Patients randomized to the control arm will receive conventional rewarming strategies such as FAWB and 2 warmed blankets.

5.3.3.5 Intervention arm

If the patient is randomized to receive the intervention, the two Ready-Heat® blankets will be activated by opening the seal on the packaging and given to the trauma team in the trauma bay. As this is an open-label trial, only the statistician will remain blinded during the final analysis. Subjects in the control arm will have a warmed blanket obtained from a blanket warmer appliance in the trauma bay.

Temporary removal of the blanket and partial exposure of the patient may be necessary to facilitate clinical procedures. In the intervention arm, two separate Ready-Heat four-panel blankets will be used to allow for temporary exposure for clinical procedures while still maintaining coverage for the rest of the body. Clinicians will be educated to keep the interventional products until the 8 hours post blanket application are completed. If an interventional product becomes soiled before the prescribed 8 hour period, a replacement product may be dispensed by contacting the Blood Bank. If there is a need to remove the intervention prior to the completion of 8 hours, the clinical team will document the reason (e.g., adverse reaction, interference with procedure, etc.). In this case, clinical teams will be educated to transition to the current standard of care (warmed blankets, or FAWB). If at least one of the two blankets remained until 8 hours post, clinical teams will be instructed to remove them and apply the current standard of care.

5.3.5.2 Storage and Stability

As per manufacturer's Instructions for Use (IFU) document, the Ready-Heat® blanket may be stored in its air-tight protective packaging until ready for use. Upon removing the outer packing, the product will reach operating temperature within 15-20 minutes and will remain functional for up to 10 hours. After use, the blanket can be disposed of with regular waste as there are no harmful ingredients. The Blood Bank will maintain a stock of the Ready-Heat® blankets and stored at room temperature. The study product will be dispensed to those randomized to the intervention arm along with the first MHP pack of blood products.

5.3.5.3 Dispensing of Investigational Product

The Ready-Heat® blanket will be provided to randomized patients by Study research coordinator/assistant. An instruction sheet will be provided specifying how to apply the Ready-Heat blanket while avoiding direct skin contact. Instructions will be provided to keep the interventional products until the 8 hours post blanket application is completed.

5.3.5.4 Return and Destruction of Investigational Product

Trauma Team members will be made aware of their responsibility to return any unused investigational products in the event the resuscitation is ended before applying the product (i.e.: patient death, termination of resuscitation). As per manufacturer's Instructions for Use (IFU) document, the Ready-Heat® blanket may be disposed of with regular waste as there are no harmful ingredients.

5.4 Study Visits and Assessments

Study visits will be conducted by research assistants during weekdays to collect data

5.4.1 Study Visits

The following information will be collected during study visits either in person or remotely reviewing electronic health records. During weekdays, 8 am to 8 pm, the research assistant will be following the patient across the different phases/locations of care and will be collecting data at the same time. Research assistants will access all documented data on the next weekday. Visits and specific data collection are detailed as follows:

5.4.1.1 Visit 1

On admission to the trauma bay: Demographics, injury characteristics and surgical management:

1. Date of injury
2. Time of injury
3. Sex
4. Age
5. Types of surgical procedures performed in the first 8 hours following hospital arrival
6. Date of arrival
7. Time of arrival
8. Time of randomization
9. Name of attending TTL and sub-TTL (if applicable)
10. Initial temperature recorded
11. Was the blanket placed on the patient? Yes/No
12. Time that the blanket was placed on the patient, if registered
13. Reason why blanket was not applied
14. Blanket applied directly to the patient's skin? Yes/No
15. Use of fluid warmers
16. Use of FAWB

5.4.1.2 Visit 2

Within the first eight hours of blanket application:

1. Location of the patient
2. Is the blanket kept on the patient? (Yes/No)
3. If not, what was the reason it was removed?
4. Temperature recorded, hourly (Yes/No)
5. If yes, the temperature recorded
6. Type of temperature measurement
7. Blanket applied directly to patient's skin? Yes/No
8. Use of FAWB
9. Use of fluid warmers

At discretion of the clinician, within the first eight hours of blanket application:

10. Coagulation (platelet count, INR, fibrinogen)
11. Perfusion parameters (pH, base deficit, serum lactate)
12. Hemoglobin

13. Number of units of red blood cells, plasma, platelets, and fibrinogen concentrate administered within the first 8 hours

5.4.1.3 Visit 3

At 24 hours post blanket application:

1. Number of units of red blood cells, plasma, platelets, and fibrinogen concentrate administered within the first 24 hours
2. Type of injury (blunt/penetrating)
3. Injury Severity Score (ISS)
4. Frequency of safety events with skin

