3.3 Secondary Feasibility Outcomes

2- Feasibility of applying and keeping the 2 blankets in the trauma bay
3- Feasibility of keeping the 2 blankets in the CT scanner suite
4- Feasibility of keeping the 2 blankets in the ED
5- Feasibility of keeping at least one of the blanket in the OR or IR suite (one can be removed for procedures and re-applied at the end of the intervention)
6- Feasibility of keeping the 2 blankets in PACU (for example one blanket is removed in the OR and reapplied at the end of the procedures and kept in PACU before the patient is transferred to the ICU)
7- Feasibility of keeping the 2 blankets in the ICU up to 8 hours of until patient achieves 37.5 degrees Celsius.
8- Reasons why the blanket was not maintained at each of the next phase of care (CT scanner suite, IR suite, OR, ED, ICU)

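### The protocol's data list records one Yes/No for the blanket, but the feasibility outcomes need both a two-blanket and an at-least-one-blanket count at the same locations

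*Combined protocol and SAP*

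**What the plan says.** Section 5.3.3.2 sets the number of blankets: "Two individually wrapped 4-panel Ready-Heat® blankets will be issued to patients enrolled in the intervention arm". Section 5.1 explains that two separate blankets are used so that part of the body can be exposed while the rest stays covered. Its instruction for the end of treatment begins "If at least one of the two blankets remained until 8 hours post blanket application". One blanket on and one off is therefore a foreseen state.

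The outcomes use two different quantities:

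- Section 3.3, outcome 2, is "Feasibility of applying and keeping the 2 blankets in the trauma bay". Outcomes 3, 4, 6 and 7 likewise ask for both blankets, in CT, the ED, PACU and the ICU.
- Section 3.3, outcome 5, is "Feasibility of keeping at least one of the blanket in the OR or IR suite", with removal and re-application of the other allowed.
- Protocol Summary, primary outcome (4), asks for at least one blanket across the trauma bay, ED, CT, OR, IR and ICU.
- Section 9.1 puts patients with at least one blanket applied into the per-protocol analysis.
- Section 6.1, criterion 2, declares the study not feasible if application and maintenance in the trauma bay fail in more than 20% of the intervention arm. It gives no blanket count.

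The data list in section 5.4.1 has these items:

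- Visit 1, item 11: "Was the blanket placed on the patient? Yes/No"
- Visit 2, item 1: "Location of the patient"
- Visit 2, item 2: "Is the blanket kept on the patient? (Yes/No"
- Visit 2, item 3: "If not, what was the reason it was removed"

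It lists no count, no item per blanket, no time of removal or re-application, and no rule for the answer when one of the two is on.

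**The concern.** A patient with one blanket on has no defined answer. Yes overstates the outcomes that need both blankets, and No understates those that need at least one. Unless a convention is set, each data collector will adopt one, and the reported retention rates will partly reflect that habit.

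Retention of the blankets is a central question of this pilot. Outcomes 2 to 7 in section 3.3, primary outcome (4) in the Protocol Summary, membership of the per-protocol set and one of the three feasibility criteria in section 6.1 all rest on these items. A count that was not recorded at the time can be recovered later only for some patients, from charts or worksheets.

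**Working it through.** **Requirement by location**

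| Location | Section 3.3 | Protocol Summary, outcome (4) |
|---|---|---|
| Trauma bay | both | at least one |
| ED | both | at least one |
| CT | both | at least one |
| OR / IR | at least one | at least one |
| PACU | both | not listed |
| ICU | both | at least one |

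Four locations (trauma bay, ED, CT, ICU) need both quantities.

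**What a Yes/No item can carry**

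| Blankets on | Both on? | At least one on? | Answer if Yes means both | Answer if Yes means at least one |
|---|---|---|---|---|
| 0 | no | no | No | No |
| 1 | no | yes | No | Yes |
| 2 | yes | yes | Yes | Yes |

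If Yes means both, states 0 and 1 merge and the at-least-one quantity is lost. If Yes means at least one, states 1 and 2 merge and the both-on quantity is lost. If Yes means both everywhere except the OR and IR, outcomes 2 to 7 can be derived, but primary outcome (4) cannot, because states 0 and 1 still merge at the four shared locations. Visit 1 has the same conflict: outcome 2 concerns applying both blankets, and the per-protocol set needs at least one applied.

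**The plan's own figures (context only).** Section 7.1 sizes the trial on 80% compliance within ±10 points. The exact binomial probability that the sample proportion falls within 0.10 of 0.80 at n = 57 is 0.95529, as printed. With 29 per arm and 20% dropout, 29/0.8 = 36.25, rounded up to 37 per arm, or 74. Nothing here depends on how blankets are counted.

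**Possible size.** The documents give no rate for exactly one blanket on, so the following is assumed. If the rate at a location is 5% to 30%:

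- Of 37 intervention patients: 37 × 0.05 = 1.9 to 37 × 0.30 = 11.1.
- Of 29 completers: 29 × 0.05 = 1.5 to 29 × 0.30 = 8.7.

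The both-on and at-least-one rates then differ by 5 to 30 percentage points. For comparison, the 95% half-width at 80% is 1.96 × √(0.8 × 0.2/37) = 12.9 points with 37 patients and 1.96 × √(0.8 × 0.2/29) = 14.6 points with 29.

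**Criterion 2, hypothetical case.** Twenty percent of 37 is 7.4, so 7 failures meet the criterion and 8 do not. Suppose 3 patients have no blanket maintained in the trauma bay and 5 have exactly one. Counting at least one as success gives 3/37 = 8.1% failures, which meets the criterion. Requiring both gives 8/37 = 21.6%, which does not.

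**The case against.** Several points on the other side have force.

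- **The CRF is not in the documents.** Section 5.4.1 is a list of information to collect. Section 13.4.1 names a separate CRF as the main instrument, and section 13.2 includes worksheets among the source documents. Either may hold more detail. This stands, so the point concerns the protocol's data list only. A reader might infer that the CRF itself is deficient; the documents do not show that.
- **Location is recorded.** A reader might infer that no Yes/No item could ever deliver outcomes 2 to 7. That is too strong, because a location-specific meaning of Yes would serve those outcomes taken alone. No such rule is stated, however, and it would still fail primary outcome (4).
- **Other records may help.** On weekdays from 8 am to 8 pm a research assistant follows the patient, and sections 5.1, 5.3.3.5 and 5.6 ask for reasons when the intervention is removed or not in use. It is therefore wrong to call the count irrecoverable for everyone. But nothing requires those records to give a count, and the Visit 2 reason is asked only after a No and does not say which blanket came off.
- **Size.** Assuming each blanket stays on independently with probability p, exactly one is on with probability 2p(1−p): 42%, 32% and 18% for p = 0.7, 0.8 and 0.9. A reader might take such figures as an estimate for this trial. The documents support neither the values of p nor independence; an adverse reaction, for instance, could plausibly lead to removal of both.
- **Decision impact.** Outcomes 3 to 7 have no success thresholds, and section 3.2 names enrolment as the primary feasibility outcome. Only criterion 2 of section 6.1 turns directly on blanket status. This limits the consequence but leaves the stated outcomes unsupported.

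**Conclusion.** The point holds for the protocol's data list as written. The listed items cannot supply both the both-on and the at-least-one quantities in the trauma bay, ED, CT and ICU, where section 3.3 and the Protocol Summary between them require both. For outcomes 2 to 7 alone the gap is a missing definition of Yes; once primary outcome (4) is included, the limit lies in the two-valued item itself. The trauma-bay criterion and the per-protocol set are affected too.

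This conclusion needs no assumption about retention; it applies at any non-zero one-blanket rate. The effect on reported rates is unknown. The range of 2 to 11 of 37 patients rests wholly on the assumed 5% to 30% and is an illustration. The change should be made before data are collected, unless the CRF already records a count.

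**What to change.** Keep the existing Visit 1 and Visit 2 items for both arms. Item 11 names no arm and is the only listed item that could capture placement of the control blankets, so it should not be replaced. For the intervention arm, add:

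- Visit 1: *Number of Ready-Heat blankets placed (0/1/2)*.
- Visit 2: *Number of Ready-Heat blankets on the patient (0/1/2)*, recorded for each location of care and whenever a blanket is removed or re-applied. An hourly count alone could miss a short CT stay or a removal between checks.
- The reason, asked whenever the count is below 2, which also serves outcome 8.

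Then state the derivations. Outcomes 2 to 4, 6 and 7 come from a count of 2. Outcome 5, primary outcome (4) in the Protocol Summary and per-protocol membership come from a count of 1 or more. State in section 6.1 which count criterion 2 uses. If the CRF already has these fields, bring section 5.4.1 into line with it.

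The cost is a few extra data fields, some added recording at transfers and matching protocol wording. Sample size stays at 74, and no clinical instruction changes.
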